### 11.3 Variables to be analyzed descriptively

#### 11.3.1 Subject disposition

- Number of patients enrolled (total; per study center)
- Inclusion and exclusion criteria

#### 11.3.2 Demographic and baseline variables

- Age
- Gender
- Ethnicity
- Height
- Weight

- Baseline creatinine

#### **11.3.3 Comorbidities**

- Hypertension
- Atrial fibrillation/flutter
- Previous myocardial infarction
- Congestive heart failure / NYHA classification
- Diabetes
- COPD
- CKD / CKD stage
- Peripheral vascular disease
- Previous stroke
- ASA score

#### **11.3.4 Medication**

- Aspirin (ASS)
- ACE inhibitors or ARBs
- Beta-blockers
- Diuretics
- NSAIDs (except ASS)
- Statins
- Vasopressors
- Use of contrast media one week prior to surgery

#### **11.3.5 Intraoperative data**

- Surgical specialty
- Type of surgery
- Duration of surgery
- If cardiopulmonary bypass (CPB): Total CPB time / Total X-Clamp time
- Intake of Crystalloids / Colloids / Erythrocytes (EC) / Thrombocytes (TC) / Fresh frozen plasma (FFP)
- Use of cell saver
- Total blood loss
- Use of urine catheter
- Total urine output
- Episodes of hypotension (MAP < 55 mmHg for more than 5 minutes)
- Application and type of vasopressors
- Application and type of nephrotoxic agents
- Application of diuretics
- Intraoperative complications / Type of complications

#### **11.3.6 Postoperative data**

- APACHE II score
- SAPS
- Cumulative intake of Crystalloids / Colloids / Erythrocytes (EC) / Thrombocytes (TC) / Fresh frozen plasma (FFP)
- Cumulative total blood loss
- Cumulative total urinary output
- Time of urine catheter removal
- Application and type of vasopressors
- Application and type of nephrotoxic agents
- Application of diuretics
- Postoperative complications / Type of complications
- Occurrence of AKI / severity of AKI / duration of AKI / diagnosis (worst case AKI)
- Time of bladder catheter removal
- Use of RRT / Start of RRT / Modality at time of RRT initiation / Indication for initiation of RRT

## 12 Statistical Analyses

Statistical analyses will be performed according to the principles of the ICH-guideline E9 "Statistical Principles for Clinical Trials" using standard statistical software.

### 12.1 Summary of study data

Variables listed in section 11 will be analyzed descriptively.

Continuous variables: Continuous variables will be summarized using the following descriptive statistics: n (non-missing sample size), number of missing values, mean, standard deviation, median, Q25%, Q75%, maximum and minimum. Histograms or boxplots might be used for graphical presentation of the data.

Categorical variables: For categorical variables the frequency and percentages (based on the non-missing sample size) of observed levels will be reported. Bar charts might be used for graphical presentation of the data.

### 12.2 Primary analysis

In the primary analysis the incidence of AKI will be estimated together with the exact corresponding two-sided 95% confidence interval according to Clopper-Pearson.

### 12.3 Secondary analyses

All secondary analyses are considered exploratory.

Secondary outcomes (see 11.2) will be evaluated based on descriptive statistics, point estimates and corresponding 95% confidence intervals.

To detect factors that might be correlated to the occurrence of AKI, MAKE90, CKD90 (i.e. development or progression), and a persistent AKI, exploratory uni- and multivariable logistic regression analyses will be conducted (including age, arterial hypertension, diabetes mellitus, sex, type of surgery as explanatory variables).

The association between AKI (overall and by severity, duration) and postoperative outcomes including use of RRT, all-cause mortality, ICU and hospital length of stay, the occurrence of MAKE90, the development or progression of CKD90, and the estimated glomerular filtration rate (eGFR) at day 90 will be assessed descriptively. Subsequent analyses for related risk factors will be undertaken.

The impact of baseline serum-creatinine and urinary output on the occurrence of MAKE90 in patients with post-surgical AKI will be assessed by logistic regression analyses.

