	
To detect factors that might be correlated to the occurrence of AKI (e.g., type/length of surgery, use of blood products, morbidities), exploratory uni- and multivariable logistic regression analyses will be conducted.
 
For secondary outcomes, descriptive statistics, point estimates and corresponding 95% confidence intervals will be derived.
 
To quantify evidence of differences between groups given by categorical parameters, such as the type of surgery, exploratory inferential analyses will be performed, using statistical tests like t-tests, Mann-Whitney-U tests, Kruskal-Wallis tests, Chi-square tests or Fisher's exact tests, appropriate to the distributional characteristics of the endpoint.
 
Additionally, subgroup analyses will be conducted based on the type of surgery to identify variables that are correlated with the occurrence of AKI in each group.

Power calculation	
The primary aim of the study is to estimate the incidence of post-surgery AKI and to derive the corresponding exact two-sided 95% confidence interval according to Clopper-Pearson. Depending on the type of surgery, AKI incidences of 1.8-39.3% are reported in existing literature. As the width of the confidence interval increases, the closer the observed incidence of post-surgery AKI equals 50%, a rate of 40% is assumed, as a conservative approach. Using this assumption, the width of the confidence interval based on a sample size of <math>n = 10,000</math> patients and a confidence level of 95% is given by 0.019. Thus, with <math>n = 10,000</math> patients, the incidence of post-surgery AKI can be estimated with at least this precision.
 
The study also aims to detect factors that might be correlated to the occurrence of post-surgery AKI, as e.g. the type of surgery (i.e. cardiac, neurological etc.) and predefined preoperative and intraoperative factors.
 
Therefore, further exploratory analyses such as uni- and multivariable logistic regression analyses will be conducted. Given the relatively large number of different types of surgeries, a sample size of <math>n = 10,000</math> patients is sufficient to investigate the influence of this parameters on the occurrence of post-surgery AKI in a uni- and multivariable context.

Trial registration	
The trial is registered at ClinicalTrials.gov (ClinicalTrials.gov Identifier: NCT04165369).

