### Secondary objectives:

The secondary objectives of the study are:

- to evaluate the severity and duration of post-surgery AKI, as well as the use of renal replacement therapy (RRT), all-cause mortality (ICU and hospital), ICU and hospital length of stay, and the occurrence of MAKE (major adverse kidney events) and CKD (chronic kidney disease) development or progression up to 90 days after extended surgical procedures,
- to determine the effects of pre- and intraoperative factors on the occurrence of AKI,
- to determine the association between AKI and postoperative outcomes including use of RRT, all-cause mortality, ICU and hospital length of stay, and the occurrence of MAKE up to 90 days after extended surgical procedures.
- Transition from non-AKI and AKI to CKD (i.e. development or progression; CKD defined by CKD-KDIGO) at day 90.

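### SAP section 12.3 specifies only a crude comparison for the association between AKI and later outcomes, and the covariates it names for its four main regressions include no baseline kidney measure

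*SAP*

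**What the plan says.** Section 5 of the SAP lists two secondary objectives that matter here: "to determine the effects of pre- and intraoperative factors on the occurrence of AKI", and "to determine the association between AKI and postoperative outcomes including use of RRT", mortality, length of stay and MAKE up to day 90. The synopsis adds CKD development or progression to the second.

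Section 12.3 answers them in three places.

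- **Risk-factor regressions.** Exploratory uni- and multivariable logistic models are planned for AKI, MAKE90, CKD90 and persistent AKI, "including age, arterial hypertension, diabetes mellitus, sex, type of surgery as explanatory variables".
- **AKI and later outcomes.** The association of AKI (overall, by severity and by duration) with RRT, mortality, length of stay, MAKE90, CKD90 and eGFR "at day 90 will be assessed descriptively". The next sentence adds: "Subsequent analyses for related risk factors will be undertaken". It names no model, outcome or covariate.
- **One model with a kidney measure.** "The impact of baseline serum-creatinine and urinary output on the occurrence of" MAKE90 is examined by logistic regression, restricted to patients with AKI.

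The synopsis gives open examples of factors for the AKI model ("type/length of surgery, use of blood products, morbidities") and refers to "predefined preoperative and intraoperative factors". All secondary analyses are labelled exploratory.

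**The concern.** Patients with reduced kidney function before surgery may be more likely both to develop AKI and to die, need RRT or have poor kidney function at day 90. Longer operations could act in the same way. A crude comparison of AKI with non-AKI patients mixes any effect of AKI with these differences.

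The plan lets such patients in: section 7 excludes dialysis-dependent end-stage disease and kidney transplant but no other chronic kidney disease. It also collects what is needed to adjust: baseline creatinine (11.3.2), CKD stage (11.3.3) and duration of surgery (11.3.5). Yet the only method it fixes for the AKI-outcome objective uses none of them. The readers of that objective's results are the ones affected.

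**Working it through.** **1. What each specified analysis can deliver**

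| Analysis in 12.3 | AKI as exposure? | Baseline kidney measure named? |
|---|---|---|
| Regressions of AKI, MAKE90, CKD90, persistent AKI | No | No |
| AKI and postoperative outcomes | Yes, descriptive only | No |
| MAKE90 on baseline creatinine and urine output | No (AKI patients only) | Yes |
| Subsequent analyses | Not specified | Not specified |

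The third row cannot compare AKI with non-AKI, because everyone in it has AKI. The group tests listed in 12.4 are unadjusted. No specified analysis therefore gives an adjusted AKI-outcome estimate.

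**2. How large could confounding be?** The SAP gives no figure for this, so what follows is an illustration on assumed inputs:

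- CKD prevalence 10% or 20%
- AKI risk 15% without CKD
- MAKE90 risk 5% in patients with neither CKD nor AKI
- CKD-AKI odds ratio (OR) 1.5, 2, 3 or 4
- CKD-MAKE90 OR 0.7, 1, 1.5, 2, 3 or 5

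Method: odds in CKD patients = odds without CKD × OR. Average the MAKE90 risk over CKD status within AKI and within non-AKI patients, then form the crude OR.

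Worked case (prevalence 20%, both ORs 3, no true AKI effect):

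- AKI risk with CKD: 0.15/0.85 × 3 = 0.529, so 0.346.
- MAKE90 risk with CKD: 0.05/0.95 × 3 = 0.158, so 0.136.
- Non-AKI: shares 0.80 × 0.85 = 0.680 and 0.20 × 0.654 = 0.131. Risk = (0.680 × 0.05 + 0.131 × 0.136)/0.811 = 0.0639.
- AKI: shares 0.80 × 0.15 = 0.120 and 0.20 × 0.346 = 0.069. Risk = (0.120 × 0.05 + 0.069 × 0.136)/0.189 = 0.0816.
- Crude OR = (0.0816/0.9184)/(0.0639/0.9361) = 1.30, where the true value is 1.0.

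Over the whole grid:

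| CKD-MAKE90 OR | True AKI OR 1.0 appears as | True AKI OR 2.0 appears as |
|---|---|---|
| 0.7 to 5 (all) | 0.92 to 1.64 | 1.83 to 3.10 |
| 1.5 only | 1.02 to 1.12 | 2.04 to 2.24 |
| 1.0 only | 1.00 | 2.00 |

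Both extremes of the full range need 20% prevalence and a CKD-AKI OR of 4, with a CKD-MAKE90 OR of 5 (upper) or 0.7 (lower).

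**3. Is there room to adjust?** Section 7 names eight surgical domains, hence 7 parameters.

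- AKI-outcome model: AKI 1, baseline eGFR 1, age 1, sex 1, hypertension 1, diabetes 1, surgery type 7, duration 1 = 14 parameters. With n = 10,000, an assumed 5% MAKE90 gives 500/14 = 35.7 events per parameter. An assumed 1% 90-day mortality gives 100/14 = 7.1, which is thin.
- AKI risk-factor model with baseline eGFR added: 4 + 7 + 1 = 12 parameters. The incidence range of 1.8% to 39.3% in section 8 gives 180 to 3,930 events, or 15.0 to 327.5 per parameter.

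**4. Complete cases.** Section 14.1 plans no imputation. If 1% to 5% is missing independently in each of the two covariates added to the named five (baseline eGFR and duration), the AKI-outcome models lose 1 − 0.99² = 2% to 1 − 0.95² = 9.75% of patients.

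**The case against.** **Nothing here is an error of statement.** The objective asks for an association, and a descriptive comparison formally supplies one. That stands, so this is a weak choice of method and not a contradiction.

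**The covariate list is open.** Section 12.3 says including, the synopsis gives only examples, and its mention of morbidities could cover CKD stage in the AKI model. The protocol, not seen here, may list the predefined factors. A reader might infer that the SAP rules out kidney adjustment, or ignores baseline kidney function in every regression. The text supports neither reading: further risk-factor analyses are promised, and one model does use baseline creatinine. What remains is that no adjusted AKI-outcome model is specified.

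**The aim of the regressions is to detect correlated factors.** For that aim, a diabetes or hypertension coefficient that partly runs through kidney disease is not wrong, and adding a kidney measure changes its meaning. This stands. A reader might also infer that duration of surgery and blood products must be added to the AKI risk-factor model because the synopsis mentions them. They are examples, and adding them likewise changes what the other coefficients mean.

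**Adjustment could give false comfort.** Starting RRT is stage 3 AKI in Table 3 (section 11.1), and RRT is a MAKE90 component in section 11.2. A patient who starts RRT within 72 h is exposed and an event by definition, and no covariate removes that. This stands, and the fix has to deal with it.

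**Conclusion.** The point holds as a weakness in how a secondary objective is analysed. Followed as written, section 12.3 answers the AKI-outcome objective with crude comparisons, although the variables needed for an adjusted estimate are collected.

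The size and direction of any confounding are unknown. The ranges above rest wholly on assumed prevalence, risks and odds ratios, and they cover CKD alone, not extent of surgery. A reader might infer that the crude estimates will be materially too high. The document does not support that: with a weak link between CKD and MAKE90 the distortion is slight, and with an inverse link it reverses.

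The results concerned are all exploratory. The primary incidence estimate and the sample size do not depend on any of this. The change is worth making because it is cheap.

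**What to change.** 1. Keep the descriptive comparison. Add to section 12.3 exploratory logistic models for 90-day mortality, MAKE90 and CKD90 with AKI as exposure, adjusted for baseline eGFR (computed from the collected baseline creatinine), age, sex, hypertension, diabetes, and type and duration of surgery. Report crude and adjusted estimates side by side with the number analysed, and label them as associations.
2. For MAKE90, state that RRT started within 72 h counts both as stage 3 AKI and as a MAKE90 event. Report the components separately, or add a sensitivity analysis that leaves out RRT started within 72 h.
3. State that baseline creatinine enters the AKI and MAKE90 definitions, and that CKD90 development or progression is judged against baseline kidney status. The coefficient of baseline eGFR should therefore be read with caution.
4. In the four risk-factor regressions, show results with and without baseline eGFR, and say that its inclusion changes the meaning of the hypertension and diabetes coefficients.

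**Cost:** SAP wording and a few more exploratory models, with no new data collection. Some patients drop out of the adjusted models because nothing is imputed (about 2% to 10% on the assumption above). Surgery types may have to be grouped if an outcome is rare.

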## 1 Synopsis

Study-ID	04-Anlt-19
Title of the trial	Observational study to evaluate the EPI demiology of Surgical-induced Acute Kidney Injury
Acronym	EPIS-AKI
Responsible institution	Department of Anesthesiology, Intensive Care and Pain Medicine [name] [name]
Medical condition	Complications after surgery
Principle investigator	Univ.-[name]. med. [name] Department of Anesthesiology, Intensive Care and Pain Medicine University Hospital of Muenster [name] [name] [contact]; [contact]; Email: [contact]
Medical project management	[name]. med. [name] Department of Anesthesiology, Intensive Care and Pain Medicine University Hospital of Muenster [name] [name] [contact]; [contact]; Email: [contact]  Dr. med. [name] Department of Anesthesiology, Intensive Care and Pain Medicine; University Hospital of Muenster [name] [name] [contact]; [contact]; Email: [contact]
Study coordinator	Dr. oec. troph. [name] Department of Anesthesiology, Intensive Care and Pain Medicine; University Hospital of Muenster [name] [name] [contact]; [contact]; Email: [contact]
Trial type	International prospective, observational, multi-center, cross-sectional cohort study

Participating centers	This clinical trial will be carried out as an international multicenter observational cohort trial in Europe and the USA. If necessary, further qualified trial sites may be recruited to the trial. The listing of trial sites, principal investigators, sub-investigators, and further trial staff, will be kept and continuously updated in a separate list. The final version of this list will be attached to the final report of the clinical trial.
Biometry	Dr. rer. medic. [name], M. Sc. Institute of Biostatistics and Clinical Research University of Muenster [name] [name] [contact] Email: [contact]
Funding	Unrestricted research grant from Baxter

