Key inclusion and exclusion criteria	
Inclusion criteria:
 
 
1. Age <math>\geq</math> 18 years
 
2. Major surgeries with a duration of at least 2 h
 
3. Planned or unplanned admission to the ICU, IMC or PACU after surgery
 
4. Written informed consent
 
 
Exclusion criteria:
 
 
1. Pre-existing AKI
 
2. AKI within the last 3 months
 
3. End stage renal disease with dialysis dependency
 
4. Kidney transplant
 

Study endpoints	
Primary endpoint: Occurrence of AKI within 72h after extended surgery according the KDIGO criteria.
 
Secondary endpoints: Secondary endpoints are:
 
 
• Use of renal replacement therapy
 
• Duration of AKI (transient vs. persistent)
 
• Length of ICU stay
 
• Length of hospital stay
 
• Survival 
 
◦ ICU mortality
 
◦ Hospital mortality
 
 
 
• MAKE90 (major adverse kidney events within 90 days): combined endpoint consisting of: 
 
◦ Mortality
 
◦ renal replacement therapy
 
◦ persistent renal dysfunction defined as serum-creatinine <math>\geq</math> 1.5 times as compared to baseline serum-creatinine
 
 
 
• Transition from non-AKI and AKI to CKD (i.e. development or progression; CKD defined by CKD-KDIGO) at day 90
 

Number of subjects	To be analyzed in the trial: n=10,000
Time plan	First patient first visit (FPFV): 01/06/2020 Last patient first visit (LPFV): 30/06/2022 Last patient last visit (LPLV): 30/09/2022 Final study report: 31/12/2022
Statistical analysis	
Statistical analyses will be performed according to the principles of the ICH-guideline E9 "Statistical Principles for Clinical Trials" using standard statistical software. Analyses will be performed based on the Full Analysis Set (FAS).
 
In the primary analysis the incidence of AKI will be estimated together with the exact corresponding two-sided 95% confidence interval according to Clopper-Pearson.

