## 6 General study design and plan

The EPIS-AKI trial is an international, prospective, observational, multi-center, cross-sectional cohort study including patients that undergo extended surgical procedures.

[figure not shown]

Figure 1: Trial workflow.

Eligible patients, i.e. meeting all inclusion and none of the exclusion criteria, will be enrolled into the study (Figure 1). The visit plan is shown in Table 1.

Visit	S	B	OD	POD 1-3	Day 90
Inclusion and Exclusion criteria	X				
Demography Age, gender, race, height, weight, creatinine, comorbidities, ASA status, medication		X			
Admission diagnosis, source of admission		X			
Intraoperative data Surgical procedure (speciality, type, duration, if cardiac: CPB)			X		

/ aortic X-clamp duration), fluid status (fluid intake, transfusion, blood loss, urine output), use of cell saver, episodes of hypotension, drug application, intraoperative complications					
Postoperative data APACHE, SAPS, fluid status, drug application, postoperative complications				X	
AKI Stage, occurrence, duration, diagnosis, RRT				X	
Concomitant Medication Vasopressors, nephrotoxic agents, diuretics				X	
Mortality					X
Length of primary stay (ICU, Hospital)					X
Serum-creatinine					X
Renal recovery					X
Number of days of RRT/RRT dependence					X
MAKE (major adverse kidney events)					X

Abbreviations: S, Screening; B, Baseline, OD, operative day; POD, postoperative day; ASA, American Society of Anaesthesiology; CPB, cardiopulmonary bypass; APACHE, Acute Physiology And Chronic Health Evaluation; SAPS, Simplified Acute Physiology Score; AKI, Acute Kidney Injury; RRT, Renal Replacement Therapy; ICU, intensive care unit.

Table 1: Visit plan.

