## 8 Statistical design and sample size calculation

The primary aim of the study is to estimate the incidence of post-surgery AKI and to derive the corresponding exact two-sided 95% confidence interval according to Clopper-Pearson. Depending on the type of surgery, AKI incidences of 1.8-39.3% are reported in existing literature (Table 2). As the width of the confidence interval increases, the closer the observed incidence of post-surgery AKI equals 50%, a rate of 40% is assumed, as a conservative approach. Using this assumption, the width of the confidence interval based on a sample size of  $n = 10,000$  patients and a confidence level of 95% is given by 0.019.

Thus, with  $n = 10,000$  patients, the incidence of post-surgery AKI can be estimated with at least this precision.

The study also aims to detect factors that might be correlated to the occurrence of post surgery AKI for different types of surgical procedures (e.g. cardiac, neurological etc.). Therefore, further exploratory analyses such as uni- and multivariable logistic regression analyses will be conducted. Given the relatively large number of different types of surgeries, a sample size of  $n = 10,000$  patients is sufficient to investigate the influence of this

parameters on the occurrence of post-surgery AKI in a uni- and multivariable context and to conduct corresponding subgroup analyses (e.g. cardiac surgery induced AKI).

Study	Year	Design	Population (n)	Definition	Incidence (%)
AKI after major abdominal surgery					
Armstrong et al. 	2009	Retrospective	Hepatobiliary (1535)	AKIN/ SCr	5.1
Bell et al. 	2014	Interrupted time series analysis	Major abdominal/GI (3271)	KDIGO/ SCr	9.8
Bihorac et al. 	2009	Retrospective	Major abdominal/GI (2337)	RIFLE/ SCr	39.3*
Biteker et al. 	2014	Prospective	Major abdominal/GI (510)	RIFLE/ SCr and GFR	7.1*
Brunelli et al. 	2012	Retrospective	Major abdominal/GI (1912)	AKIN/ SCr	26.8*
Causey et al. 	2011	Retrospective	Colorectal (339)	RIFLE/ SCr	11.8
Chao et al. 	2013	Retrospective	Major abdominal/GI (1972)	AKIN/ SCr	20.2
Cho et al. 	2014	Prospective	Hepatobiliary (111)	AKIN/ SCr and UO	1.8*
Coca et al. 	2010	Retrospective	Major abdominal/GI (11460)	AKIN/ SCr	18.9*
Correa-Gallego et al. 	2015	Retrospective	Hepatobiliary (2116)	RIFLE/ GFR	15.9

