### 12.5 Subgroup analyses

Exploratory subgroup analyses will be performed based on the type of surgery (e.g. cardiac surgery) to identify variables that are correlated with the occurrence of AKI (overall and by severity) in each group.

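### The exploratory risk-factor regressions in SAP 12.3 and 12.5 specify no centre term or clustering adjustment for an international multicentre cohort

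*SAP*

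**What the plan says.** The design is an "international, prospective, observational, multi-center, cross-sectional cohort study" (SAP section 6), run as an "international multicenter observational cohort trial in Europe and the USA" (Synopsis), and further sites may be added. The planned size is given as "To be analyzed in the trial: n=10,000".

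For the factors behind AKI, MAKE90, CKD90 and persistent AKI, section 12.3 states that "exploratory uni- and multivariable logistic regression analyses will be conducted", "including age, arterial hypertension, diabetes mellitus, sex, type of surgery as explanatory variables". Section 12.5 repeats the exercise within types of surgery, "to identify variables that are correlated with the occurrence of AKI (overall and by severity) in each group". Section 12.4 calls two-sided p-values of 0.05 or below statistically noticeable.

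In the analysis sections, centre is used only as an enrolment count in 11.3.1: "Number of patients enrolled (total; per study center". Nothing in the SAP names centre or country as a model term, a stratum, a random effect or a cluster for variance estimation.

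**The concern.** Section 5 makes the effects of pre- and intraoperative factors on AKI a secondary objective, and these regressions are the analysis that serves it. As written, they treat 10,000 patients from many hospitals as independent and unstratified. Two separate problems can follow.

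1. **Precision.** If centres differ in AKI level or in how completely they detect AKI, patients in one centre resemble each other. For a factor that also varies by centre, the ordinary standard error is then too small.
2. **Confounding.** If centres with more of a given surgery type or practice also tend to have a higher or lower recorded AKI level, the pooled odds ratio mixes the factor with the centre. A larger sample does not remove this.

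Both are plausible here. Hospitals specialise, and section 7 targets eight surgical domains. Several intraoperative variables in 11.3.5 (vasopressors, colloids, cell saver) are likely to follow local practice. KDIGO staging depends on creatinine and urine-output capture, and section 14.1 excludes imputation. With 10,000 patients, even a small distortion can pass the 0.05 mark.

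**Working it through.** **The plan's own figure.** The only sizing figure is the width of the Clopper-Pearson interval for the primary incidence, for which "a rate of 40% is assumed, as a conservative approach" (section 8). With x = 4,000 and n = 10,000 the limits are 0.3904 and 0.4097, a width of 0.0193. The stated 0.019 reproduces. The SAP gives no corresponding figure for the regressions, so everything below rests on assumed centre inputs.

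**Confounding by hand.** Assume two equal centre types that record AKI in 35% and 20% of patients. Surgery type A makes up 70% and 30% of their patients, and type has no effect within either.
- Type A: 0.7 × 0.35 + 0.3 × 0.20 = 0.305
- Other types: 0.3 × 0.35 + 0.7 × 0.20 = 0.245
- Pooled OR = (0.305/0.695) / (0.245/0.755) = 1.35
- With 5,000 per group, SE(log OR) = √(1/1525 + 1/3475 + 1/1225 + 1/3775) = 0.045, so the 95% CI is 1.24 to 1.48.

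With 25% versus 20% the proportions are 0.235 and 0.215, and the OR is 1.12 (1.02 to 1.23). The true within-centre OR is 1 in both cases.

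**How it depends on the correlation.** Assume 30 centres, about 10,000 patients, intercept log(0.25), centre log-odds SD 0.2, exposure logit SD 1 and no within-centre effect. Fit the pooled logistic model.

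| Correlation of centre exposure with centre AKI level | Mean pooled OR | p ≤ 0.05 |
|---|---|---|
| 0 | 1.00 | about 7% |
| 0.2 | 1.03 | about 16% |
| 0.5 | 1.08 to 1.09 | 35 to 40% |

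The range in the last row comes from two runs. One had 60 replicates (Monte Carlo SE √(0.35 × 0.65/60), about 6 points) and the other 400. A further repeat with 1,000 replicates and an average exposure of one half gave ORs of 1.00, 1.03 and 1.08, with 10%, 14% and 37% flagged. With a smaller exposure spread (logit SD 0.5), correlations of 0.2 and 0.5 give ORs of 1.02 and 1.05, with 8% and 16% flagged.

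With centre SD 0.4 and correlation 0.5, the OR is about 1.17 and 82% are flagged. At correlation 0 the OR shows no bias, but 12 to 22% are still flagged. With centre in the model (correlation 0.5, 60 replicates), the mean OR is 1.00 and 5 to 7% are flagged at either SD.

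**A second layout.** Assume 100 centres of 100 patients, 150 replicates, and exposure logit SD 1 to 2. The centre SD is √(ICC/(1 − ICC) × π²/3), which is 0.18, 0.42 and 0.60 for ICC 0.01, 0.05 and 0.10.

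| ICC | Correlation 0: OR; flagged | Correlation 0.5: OR; flagged |
|---|---|---|
| 0.01 | 1.00 to 1.01; 5 to 7% | 1.09 to 1.12; 31 to 59% |
| 0.05 | 1.00; 5 to 19% | 1.18 to 1.28; 82 to 97% |
| 0.10 | 1.00 to 1.01; 17 to 32% | 1.28 to 1.42; 97 to 100% |

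The centre-stratified Mantel-Haenszel OR stays between 0.99 and 1.01 throughout.

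**The case against.** The strongest reply has four parts.

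- **The covariate list is open.** It is introduced by the word including, and the Synopsis mentions length of surgery, blood products and morbidities as further candidates. A reader might infer that the SAP rules centre out; it does not. It leaves centre unspecified, and the specified analysis is an ordinary logistic model.
- **Bias is conditional.** A reader might infer that the odds ratios will absorb centre differences. The documents do not support that, because they give neither the between-centre variation nor its correlation with case mix. At correlation 0 the odds ratio is unbiased, and at ICC 0.01 the false-flag rate is close to nominal.
- **Differential detection is inferred.** Section 4 attributes missing urine output to existing databases, and the Synopsis answers with prospective KDIGO criteria and a standardised data collection instrument. Nothing shows that this study's centres differ in catheter use or creatinine frequency.
- **The analyses are exploratory.** Section 12.4 limits their interpretation to that level and allows further analyses on demand.

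All four stand as limits on size and certainty. They do not remove the point. Handling of centre belongs in the model specification, and leaving it to a later choice made with the data in hand is what a SAP should prevent. One further limit applies to 12.5: within a single type of surgery, confounding of the surgery-type contrast cannot arise, so the point there concerns practice-dependent factors and standard errors. The illustrations do not cover that case.

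**Conclusion.** The concern holds as a gap in the specification of the exploratory regressions. Standard errors will be too small for factors that vary by centre once between-centre variation in AKI level or detection is appreciable. Odds ratios for surgery type and practice-dependent factors will be confounded only if case mix or practice also correlates with that level.

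The size cannot be derived from the SAP. Under modest assumed variation (centre SD 0.2) the shift in a null odds ratio runs from none to about 1.09, depending on the correlation. Larger assumed variation gives more. The highest false-flag rates above rest on an assumed correlation of 0.5 and are not predictions for this study.

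A reader might also take this as a defect in the primary result. It is not: the primary point estimate is a single proportion and does not depend on these models.

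**What to change.** In 12.3 and 12.5, state that the multivariable logistic models include a random intercept for centre and that these give the main adjusted odds ratios. Add a within-centre model (centre as a fixed effect, or conditional logistic regression stratified by centre) as a sensitivity analysis where event counts allow. The second model is needed because a random intercept alone may not remove all centre-level confounding. The within-centre model should not lead, because the conditional or fixed-effect fit gets no information from centres without events, which matters for rarer outcomes such as persistent AKI and in the subgroups.

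The cost is a few sentences in the SAP and standard models in R, the software named in section 16. Centre is already recorded. Intervals will be somewhat wider. In the within-centre check, centres with only one surgery type add nothing to the surgery-type contrast, and centres with no events do not contribute.
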